Statistical Considerations:	
The following statistical analyses are planned:
 
 • Odds ratio of antibiotic prescription between 2 groups as well as the difference in proportion of patients prescribed an antibiotic by day 28 using logistic regression corrected for variation at the GP level (generalized linear mixed effect) • Difference between the mean number of days with restricted activities by day 7 using linear mixed effect regression • Difference between the mean number of medical consultations by day 28 using linear mixed effect regression • Odds ratio of the risk of adverse outcomes between 2 groups as well as the difference in proportion of patients with adverse outcomes and clinical failure using logistic regression corrected for variation at the GP level (generalized linear mixed effect) • Difference between the mean daily symptom scores measured in the different arms. The effects of the interventions on recovery will be studied by comparing the slopes of symptom scores over time between arms • Difference in the mean duration of total time spent in the practice using linear mixed effect regression • Difference in levels of satisfaction of providers and patients between arms • Difference in the mean cost per arm using linear mixed effect regression • Diagnostic performance of: 
 ◦ individual host biomarker(s) based on crude positive and negative likelihood ratios, and on the area under the curve of receiver operator characteristic (ROC) curves, to predict the development of a serious adverse outcome, a clinical failure, or the presence of pneumonia ◦ combined biomarkers based on sensitivity and specificity generated by classification and regression trees (CART) analyses, to predict the development of a serious adverse outcome, a clinical failure, or the presence of pneumonia
GCP Statement:	This study will be conducted in compliance with the protocol, the current version of the Declaration of Helsinki, the ICH-GCP as well as all national legal and regulatory requirements.

ABBREVIATIONS

ARI	Acute Respiratory tract Infection
ASR	Annual Safety Report
CAP	Community Acquired Pneumonia
CEC	Competent Ethics Committee
CHUV	Centre Hospitalier Universitaire Vaudois
COPD	Chronic Obstructive Pulmonary Disease
CRP	C-reactive protein
CT	Computerized Tomography
CTU	Clinical Trials Unit
CXR	Chest X-ray
eCRF	Electronic Case Report Form
FOPH	Federal Office of Public Health

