An individual patient may also choose to refuse the phone interview, without discontinuing the study itself. In this case, the investigators can access the medical file until the end of the 28 days observation period.

There are no foreseeable reasons for investigators to withdraw a patient from the study. Patients who are not reachable during follow-up will not have outcome data. They will be excluded from the analysis of the safety of the intervention but they will still be included in the assessment of impact on antibiotic treatment and of the feasibility of the intervention.

Physicians may choose to discontinue participating in the study. If so, they are responsible of informing the study team. If discontinuation occurs before the training and randomisation session, they will be replaced by another willing physician. If discontinuation occurs after patient recruitment, training and randomisation, patient outcomes will be collected by the study staff until the end of planned follow-up. Access to the medical files will be discussed on a case by case basis with the physician.

There is no foreseeable reason for the investigators to withdraw a physician from the study once he participated in patient recruitment, training and randomisation.

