9.2 Assessments of outcomes

Assessment of primary outcome

Pilot Study

Assessment of the outcomes of the pilot study has been described in section 8.5.1.

Randomized intervention study

Assessment of the outcomes of the randomized intervention study has been described in section 8.5.2.

Assessment of secondary outcomes

Pilot Study

Assessment of the outcomes of the pilot study has been described in section 8.5.1.

Randomized intervention study

Assessment of the outcomes of the randomized intervention study has been described in section 8.5.2.

Assessment of other outcomes of interest

Assessment of the exploratory outcomes has been described in section 8.5.2.3

Assessment of safety outcomes

Adverse events

The GP will be asked to record any serious adverse events (hospitalization, death) within 7 days into the eCRF. Any new recording of severe adverse events (SAE) will be automatically notified to the PI. Adverse events recorded by telephone follow-up will also be recorded

Laboratory parameters

In the intervention arms, prescription of laboratory tests (other than PCT POCT) will be at the discretion of the participating physicians. They will follow their usual routine, either for tests performed in house or sent to an external laboratory. No additional quality control or standard procedures are planned for this aspect.

Vital signs

Vital signs will be assessed with the usual equipment available to the GP at his practice. Measurement is expected to reflect routine practice, and as such no standardized measurement protocol or calibration procedures are planned.

Assessments in participants who prematurely stop the study

Patients will be considered lost to follow-up if telephone interviews were not feasible. A patient may change GP over the course of the study, without this affecting his participation in the study. Phone interviews will continue.

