11.4 Planned Analyses

Datasets to be analysed, analysis populations

The analysis will be performed in intention to treat (pragmatic trial). The analysis population will comprise all patients included by the randomised GPs. The primary analysis will include all patients enrolled in the study, irrespective of follow-up. Patients who are lost to follow-up will be considered as having had a clinical failure, an adverse outcome and duration of disease equal to the maximum duration measured in the other patients. Patients in whom GPs did not follow the respective algorithm recommendation and/or who did not have complete telephone follow-up will be excluded from the per-protocol analysis.

Primary Analysis

Odds ratio of antibiotic prescription between 2 groups as well as the difference in proportion of patients prescribed an antibiotic by day 28 using logistic regression corrected for variation at the GP level (generalized linear mixed effect)

Secondary Analyses

The following statistical analyses are planned:

- Difference between the mean number of days with restricted activities by day 14 using linear mixed effect regression
- Difference between the mean number of medical consultations by day 28 using linear mixed effect regression
- Odds ratio of adverse outcome between 2 groups as well as the difference in proportion of patients with adverse outcome and clinical failure using logistic regression corrected for variation at the GP level (generalized linear mixed effect)
- Difference between the mean daily symptom scores measured in the different arms. The effects of the interventions on recovery will be studied by comparing the slopes of symptom scores over time between arms
- Difference in the mean duration of total time spent in the practice using linear mixed effect regression
- Difference in levels of satisfaction of providers and of patients between arms
- Difference in the mean cost per arm using linear mixed effect regression
- Diagnostic performance of:
 - individual host biomarker(s) based on crude positive and negative likelihood ratios, and on the area under the curve of receiver operator characteristic (ROC) curves, to predict the development of a life-threatening disease, clinical failure, or the presence of pneumonia (using a clinical diagnosis).

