 - combined biomarkers based on sensitivity and specificity generated by classification and regression trees (CART) analyses, to predict the development of a life-threatening disease, clinical failure, or the presence of pneumonia (using a clinical diagnosis).

For each arm of the study, socio-demographic and clinical characteristics will also be described.

Interim analyses

For quality and safety purposes, interim analyses will be performed after inclusion of 50 patients in each of the intervention and control arms. The results of the interim analysis will be reviewed by the steering committee.

Safety analysis

An annual safety analysis will be done by the study coordinator, comparing the incidence of clinical failure by day 7, hospital admissions and deaths between both groups. This will be included in the annual safety report.

Adverse events will be reported to the steering committee within seven days.

Deviation(s) from the original statistical plan

Any deviation from the original statistical plan will be justified and reported in the final study report.

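### The rule coding lost patients as failures is not limited to arm comparisons, so it would add patients of unknown outcome to the cases in the biomarker accuracy analyses for clinical failure

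*Combined protocol and SAP*

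**What the plan says.** Section 11.4, in its opening paragraph on datasets and analysis populations, sets one rule: "Patients who are lost to follow-up will be considered as having had a clinical failure, an adverse outcome". It makes no exception for any analysis listed below it.

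Under Secondary Analyses, the same section plans accuracy analyses for "individual host biomarker(s) based on crude positive and negative likelihood ratios, and on the area under the curve of receiver operator characteristic (ROC) curves" and for "combined biomarkers based on sensitivity and specificity generated by classification and regression trees (CART) analyses". The targets there are "to predict the development of a life-threatening disease, clinical failure, or the presence of pneumonia (using a clinical diagnosis". The synopsis (Statistical Considerations) names the second target differently: "to predict the development of a serious adverse outcome, a clinical failure, or the presence of pneumonia". Section 5.2 also uses serious adverse outcome.

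Three other places bear on the point:
- Section 7.2 (criteria for withdrawal) says "Patients who are not reachable during follow-up will not have outcome data" and "They will be excluded from the analysis of the safety of the intervention". It keeps these patients for the antibiotic and feasibility assessments and does not mention the accuracy analyses.
- Section 9.2 defines the group: "Patients will be considered lost to follow-up if telephone interviews were not feasible".
- Section 11.5 expects some loss by telephone but gives neither a rate nor a rule for outcomes missing because of it.

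**The concern.** Counting unknown outcomes as failures is a stress test for a comparison between arms. In an accuracy analysis the outcome is the reference standard, so the same coding creates cases that nobody observed. Sensitivity, both likelihood ratios and the AUC are then computed partly on those patients, and a tree can choose its splits to separate them.

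The rarer the true outcome, the larger the share of cases that the rule creates. A useful marker could look weak. If loss is related to the marker, a weak marker could look useful. Either way the estimate would describe a mixture of clinical failure and being unreachable by telephone.

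**Working it through.** The plan states no AUC, sensitivity or precision target for the biomarker analyses, so there is no figure to reproduce.

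**Which targets the rule reaches**

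| Target in 11.4 | Named in the lost-to-follow-up rule? | Reached? |
|---|---|---|
| Clinical failure | Yes | Yes |
| Life-threatening disease | No; the rule says adverse outcome | Only if it means the serious adverse outcome of the synopsis and 5.2 |
| Pneumonia by clinical diagnosis | No | No |

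**Inputs**
- Patients with marker blood: N = 420, that is 2 × 210. Section 11.2 gives 210 per arm, and Section 8.1 says venous blood is not collected in usual care.
- Event risk p: 0.05 is the planning value in 11.2 for the composite adverse outcome under usual care. No rate is given for day-7 clinical failure, so p = 0.10 and 0.20 are added as assumptions.
- Loss rate l: not given. Assumed 3, 5 and 10%.
- True AUC 0.80: assumed.
- Lost patients have the marker distribution of non-cases: assumed here and varied below.

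**Formula**

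The AUC is the probability that a case has a higher marker value than a non-case, so it averages linearly over the two kinds of labelled case. Let w be the share of labelled cases that are real:

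w = (1 − l)p / [(1 − l)p + l]

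Observed AUC = 0.80w + 0.50(1 − w)

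Example with p = 0.05 and l = 0.05:
- Real cases observed: 420 × 0.95 × 0.05 = 20.0. Lost patients: 420 × 0.05 = 21.0.
- w = 20.0/41.0 = 0.49.
- AUC = 0.80 × 0.487 + 0.50 × 0.513 = 0.646.

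| Event risk | 3% loss | 5% loss | 10% loss |
|---|---|---|---|
| 5% | w 0.62, AUC 0.69 | w 0.49, AUC 0.65 | w 0.31, AUC 0.59 |
| 10% | w 0.76, AUC 0.73 | w 0.66, AUC 0.70 | w 0.47, AUC 0.64 |
| 20% | w 0.87, AUC 0.76 | w 0.79, AUC 0.74 | w 0.64, AUC 0.69 |

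**Check with loss independent of outcome**

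If loss is unrelated to outcome, a fraction p of the lost are true cases, and the real share becomes p / [(1 − l)p + l]. At p = 0.05 this is 0.051 / 0.099 in rounded terms (0.05/0.0975 = 0.513) for 5% loss and 0.05/0.145 = 0.345 for 10% loss. The AUC is 0.65 and 0.60, almost the same as above.

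Now assume true sensitivity 0.80 and specificity 0.75. Observed sensitivity is 0.80t + 0.25(1 − t), where t is the real share:
- 5% loss: sensitivity 0.53; LR+ falls from 3.20 to 0.53/0.25 = 2.13; LR− rises from 0.27 to 0.62.
- 10% loss: sensitivity 0.44, LR+ 1.76, LR− 0.75.

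Specificity stays at 0.75, because the labelled non-cases are still a fair sample of non-cases.

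**Direction of the bias (p = 0.05, l = 0.10, binormal markers)**

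The value 0.50 in the AUC formula is replaced by the AUC of lost patients against non-cases.

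| Marker level of lost patients | Observed AUC (true 0.80) |
|---|---|
| 0.5 SD below non-cases | 0.50 |
| Same as non-cases | 0.59 |
| Same as true cases (1.19 SD above non-cases) | 0.80 |
| 1.5 SD above non-cases | 0.84 |

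**The case against.** The best defence is that the rule was never meant for these analyses. It stands in a paragraph on the intention-to-treat and per-protocol sets, which concern arms, and Section 7.2 says unreachable patients have no outcome data. A sensible analyst might leave them out unprompted. This has force as to intent. On the text, however, the 11.4 rule has no limit, and 7.2 removes these patients only from the safety analysis. Only the per-protocol set drops patients with incomplete telephone follow-up, and the accuracy analyses are not assigned to it.

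Loss may also be small. Section 7.2 allows use of the medical file for patients who refuse the interview, GPs record admissions and deaths within 7 days (9.2), and visits for deterioration generate an eCRF (8.5). That stands, and no loss rate is given. It also has another side: under the 9.2 definition, a patient who declined the telephone interview could be counted as lost, and so as a failure, although the file documents a good outcome.

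A reader might infer that every AUC, sensitivity and tree is pulled towards chance and that the biomarker objective would fail. The documents do not support this:
- The pneumonia target, a stated part of that objective, is outside the rule.
- Attenuation requires lost patients to have marker values well below those of true cases. The documents do not say who is lost, and patients may be unreachable because they were admitted or died.
- The 5% risk belongs to the adverse outcome in usual care, an arm without marker blood. Day-7 clinical failure also counts lack of improvement in fever or dyspnoea (5.2), so its rate may well be higher and the distortion smaller.

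**Conclusion.** The concern holds in a limited form. As written, 11.4 puts patients of unknown outcome into the case group for clinical failure, and for the second target if that target is the serious adverse outcome. Nothing elsewhere in the plan prevents this.

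If lost patients look like non-cases, a true AUC of 0.80 would be reported as about 0.59 to 0.69 at 5% event risk and 0.69 to 0.76 at 20%, for 10% down to 3% loss. The loss rates, the true AUC, the higher event risks and the marker distribution of lost patients are all assumptions. The direction of the bias is not fixed either: it is nil if lost patients resemble true cases and upward if their markers are higher still.

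The analyses are exploratory in purpose, although 11.4 lists them under secondary analyses, and they involve about 420 patients. The primary outcome is not at stake. The point is still more than a missing detail, because a stated rule, if followed, can give a wrong result, and correcting it costs almost nothing.

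**What to change.** Add to 11.4: *The rule that counts patients lost to follow-up as failures applies only to comparisons between arms. In the diagnostic and prognostic accuracy analyses, patients whose outcome is unknown from all sources (telephone, diary, GP eCRF, medical file) are treated as missing, with multiple imputation as a sensitivity analysis.*

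In the same edit:
- Use one name and definition for the second biomarker target in the synopsis, 5.2 and 11.4.
- Reconcile 7.2 (no outcome data, excluded from safety) with 11.4 (counted as failure), so that it is clear where each rule applies.

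If loss is unrelated to marker and outcome, treating these patients as missing recovers the assumed AUC and sensitivity of 0.80. The cost is a few sentences and a few patients fewer in an exploratory analysis (about 21 of 420 at 5% loss). No new data are needed. Limiting the rule in this way leaves the primary outcome and the arm comparisons as they are. How 7.2 and 11.4 are reconciled for the safety comparison is a separate decision.

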11.1 Hypothesis

The null hypothesis is that there is no difference in the proportion of antibiotic prescription in patients enrolled in the different arms of the trial.

The alternative hypothesis is that combined use of POCT procalcitonin testing with lung ultrasound leads to significant reduction in antibiotic use with no difference in terms of clinical outcome, duration of the episode, activities restrictions and adverse outcomes.

A reduction of at least 15% in the proportion of patients treated with antibiotics by day 28 is expected as below this threshold, the intervention would be considered as no having a sufficient impact to warrant its implementation at larger scale, at least in its present format.

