11.5 Handling of missing data and drop-outs

Any missing data at the enrolment visit due to incomplete completion of the pre-assigned components of the algorithm will lead to the patient being assigned to the intention to treat analysis. We expect that the use of electronic CRFs using tablet computers will keep these to a minimum.

We expect some loss of patients to follow-up if they are not successfully contacted for follow-up by telephone. All efforts will be made to be made to keep these to a minimum. During follow-up, calls we will also remind patients to fill the self assessment by daily diary.

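### Sections 7.2 and 11.4 conflict on lost patients. If 11.4 governs, coding every lost patient as an event dilutes the safety odds ratio under equal loss and costs power

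*Combined protocol and SAP*

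**What the plan says.** Section 11.4 (Datasets to be analysed, analysis populations) sets the rule: "Patients who are lost to follow-up will be considered as having had a clinical failure, an adverse outcome", and also "duration of disease equal to the maximum duration measured in the other patients". It makes no distinction by arm. The same section analyses adverse outcome and clinical failure by an odds ratio and a difference in proportions from a mixed logistic model. It gives no margin or confidence-limit rule there.

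Section 7.2 (Criteria for withdrawal / discontinuation of participants) says of patients who cannot be reached: "They will be excluded from the analysis of the safety of the intervention". They stay in the antibiotic analysis.

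Section 9.2 defines loss by the telephone: "Patients will be considered lost to follow-up if telephone interviews were not feasible". For patients who decline the interview but remain in the study, 7.2 adds: "In this case, the investigators can access the medical file until the end of the 28 days observation period".

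The safety hypothesis in 11.1 is "no difference in terms of clinical outcome, duration of the episode, activities restrictions and adverse outcomes". Section 11.2 describes non-inferiority for the composite adverse outcome, with 5% in usual care and an absolute margin of 0.02. Section 11.5 says "We expect some loss of patients to follow-up", but gives neither a rate nor a method for missing outcomes.

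**The concern.** Counting lost patients as failures is usually defended as conservative, and it can be when the aim is to show benefit. Here the hoped-for safety finding is that the arms do not differ. Adding the same block of assigned events to each arm makes the arms look more alike. The trial tests two algorithms that withhold antibiotics, so these comparisons carry its safety conclusion. A real excess of failures could be reported as a much weaker association.

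The rule may also override real data. Besides the calls, the plan collects a daily diary and a GP form at unplanned visits (8.5), GP-recorded hospitalisations and deaths within 7 days (9.2), and the medical file for some patients (7.2). Under a telephone-only definition, a patient with a documented recovery could be analysed as having a serious adverse outcome.

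**Working it through.** **Inputs.** From 11.2: 14 GPs x 15 patients = 210 per arm, control risk 0.05, margin 0.02, intracluster coefficient 0.06 (stated for antibiotic prescription). Assumed, because the documents give no figure: loss L of 2% to 20%, and a raised intervention risk of 7% or 10%. Calculations use the normal approximation with unpooled variance and ignore clustering unless stated.

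**The plan's own figure.** Section 11.2 states 80% power for non-inferiority of the composite. With 5% in both arms, SE = sqrt(2 x 0.05 x 0.95 / 210) = 0.0213. Power = Φ(0.02/0.0213 - 1.96) = 15% at one-sided 0.025, or 24% at one-sided 0.05. The 80% is not reproduced. The simulation figure is not shown, so its assumptions cannot be checked. That is a separate issue; it matters here because there is little power to lose.

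**Effect on the odds ratio, equal loss.** The analysed risk is p' = p(1-L) + L. Put c = L/(1-L). Then p' = (1-L)(c + p) and 1 - p' = (1-L)(1-p), so

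OR' = [(c + p1)/(c + p0)] x [(1 - p0)/(1 - p1)].

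The second factor is unchanged by loss. The first is always closer to 1 than p1/p0, so any non-null odds ratio is attenuated. The risk difference becomes (1-L)(p1 - p0).

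| Loss | Analysed risks (true 5% v 10%) | Odds ratio | Risk difference |
|---|---|---|---|
| 0% | 5.00% v 10.00% | 2.11 | 5.00 points |
| 2% | 6.90% v 11.80% | 1.81 | 4.90 |
| 5% | 9.75% v 14.50% | 1.57 | 4.75 |
| 10% | 14.50% v 19.00% | 1.38 | 4.50 |
| 20% | 24.00% v 28.00% | 1.23 | 4.00 |

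**Power to detect 5% v 10% at 10% loss (two-sided 5%).**
- Complete cases, 189 per arm: SE = sqrt((0.05 x 0.95 + 0.10 x 0.90)/189) = 0.02697; Φ(0.05/0.02697 - 1.96) = 46%.
- Coded, 210 per arm: SE = sqrt((0.145 x 0.855 + 0.19 x 0.81)/210) = 0.03638; Φ(0.045/0.03638 - 1.96) = 23%.
- If the design effect 1 + 14 x 0.06 = 1.84 is applied to both, each SE grows by sqrt(1.84) = 1.356. Power is then Φ(1.367 - 1.96) = 28% against Φ(0.912 - 1.96) = 15%.

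**Against the 0.02 margin (one-sided 0.025, 10% loss).**
- Arms truly equal at 5%. Complete cases: SE = sqrt(2 x 0.05 x 0.95/189) = 0.0224, and the chance of showing non-inferiority is Φ(0.02/0.0224 - 1.96) = 14%. Coded: SE = sqrt(2 x 0.145 x 0.855/210) = 0.0344, and the chance is Φ(0.02/0.0344 - 1.96) = 8%.
- True difference at the margin (5% v 7%). Complete cases give 2.5% false non-inferiority. Coded risks are 14.5% and 16.3%, SE = 0.0352, and Φ((0.02 - 0.018)/0.0352 - 1.96) = 2.9%.

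**Unequal loss.** With 5% true risk in both arms, 10% loss in the intervention arm and 5% in usual care, the analysed risks are 14.5% v 9.75%, an odds ratio of 1.57. Reversing the loss gives 0.64. With true risks of 10% (intervention) and 5% (usual care), 5% loss in the intervention arm and 10% in usual care put both analysed risks at 14.5%. The odds ratio is then 1.00 and a true doubling disappears.

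**The case against.** **The coding may not be the rule.** If 7.2 prevails, no events are assigned and the dilution does not arise. This stands: a reader might infer that the problem holds however the passages are reconciled, and it does not. One could also argue that 7.2 and 11.4 concern different analyses, but neither says so. Clinical failure appears both in the coding rule and in the safety analysis of 11.4.

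**The direction depends on the decision rule.** A reader might infer that the rule simply makes the no-difference claim easier. That holds if safety is judged by a non-significant odds ratio or difference. Against the only numerical criterion, the 0.02 margin, the rule mostly hinders the hoped-for conclusion. Nor is the bias one-way once loss differs between arms.

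**The size is conditional.** On the risk-difference scale, 10% loss removes only half a point from a 5-point difference. Assigned events outnumber real ones at a 5% risk only when L > 0.05(1-L), that is, loss above 0.05/1.05 = 4.8%. Part of the extra variance is present without the coding: at 10% loss, with 5% in both arms, the fair contrast of SEs is 2.24 v 3.44 points.

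**Two readings go beyond the text.** No passage says that patients who decline the call are coded as lost; 7.2 treats them as still in the study. And the maximum-duration rule names duration of disease. It does not enter an odds ratio, and it does not name restricted activity, the duration outcome that has a margin in 11.2.

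**The per-protocol set offers some check,** because it drops patients without complete telephone follow-up. It also drops patients whose GP departed from the algorithm, so it does not isolate the effect of the coding.

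**Conclusion.** The concern holds in a conditional form. The plan contains two conflicting rules for the same patients. If the one in 11.4 governs, equal loss always attenuates the safety odds ratio: 2.11 becomes 1.81, 1.57, 1.38 and 1.23 at 2%, 5%, 10% and 20% loss for an assumed 5% v 10%. At 10% loss it roughly halves the power to see that harm. Judged by the test written in 11.4, this helps a finding of no difference. Judged against the margin in 11.2, it mainly costs power (14% to 8%) and barely changes false non-inferiority (2.5% to 2.9%). Unequal loss can push the result in either direction. The sizes rest on assumed loss rates and raised risks; the direction under equal loss follows from algebra alone. These are secondary outcomes, so the change is one that should be made, not one on which the primary result depends.

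**What to change.** 1. Reconcile 7.2 and 11.4 into one rule for patients without follow-up, and align the definition in 9.2 with it.
2. In 11.4, base the main safety analyses on outcome information from any source already collected (telephone, medical file, GP eCRF, diary). Count a patient as lost only when no source gives the outcome, and say how patients who decline the call are classified.
3. Handle the remainder under missing at random, by the mixed model or by multiple imputation that allows for GP.
4. Keep lost = failure / maximum duration as a labelled sensitivity analysis. Add one that varies the assumption by arm, for example lost intervention patients as failures and lost usual-care patients not.
5. State in 11.4 whether safety is judged by a difference test or against the 0.02 margin, and at what alpha.

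**Cost.** Plan wording and modest extra analysis; no new data. The main analysis then rests on a missing-at-random assumption, which is doubtful if unreachable patients are the sicker ones. It also rests on few events: about 0.05 x 210 = 10.5 per arm at the planned rate. The sensitivity analyses are there to probe that.
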